### 7.8.2      **Laboratory data**

The analyses of laboratory data will be descriptive in nature and will be based on BI standards "Display and Analysis of Laboratory Data" ([9](#)).

Analyses will be based on normalised values, which means transforming to a standard unit and a standard reference range. The original values will be analysed if the transformation into standard unit is not possible for a parameter.

Descriptive statistics of laboratory values over time and for the difference from baseline (see [Section 6.7](#)) will be provided. Frequency tables of changes between baseline and last value on treatment with respect to the reference range will be presented.

Unscheduled measurements of laboratory data will be assumed to be repeat measurements of the most recent scheduled measurement (e.g. for follow-up or confirmation of a particular value). Therefore, unscheduled measurements will be assigned to the planned time point of the previous scheduled measurement. Descriptive statistics will be calculated by planned time point based on the worst value of the subject at that planned time point (or assigned to that planned time point).

Possibly clinically significant abnormal laboratory values are only those identified either in the Investigator's comments or at the RPM at the latest. It is the Investigator's responsibility to decide whether a lab value is clinically significant abnormal or not. Standard or project-specific rules for flagging clinically significant values in an automated manner will not be applied in this study.

Clinically relevant findings in laboratory data will be reported as baseline conditions (prior to first administration of study treatment) or as AEs (after first administration of study treatment) if judged clinically relevant by the investigator, and will be analyzed as such.

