Urine sediment  (microscopic examination if haemoglobin, leukocytes nitrite or protein are abnormal in urine)	Only positive findings will be reported (for instance, the presence of sediment bacteria, casts in sediment, squamous epithelial cells, erythrocytes, leukocytes)			

A: parameters to be determined at Visit 1 and Visit 2 screening examination, Day -11

B: parameters to be determined at Visit 3 on Day 1, 14, 28 for Dose Group 1 and 2,

parameters to be determined at Visit 3 on Day 1, 7 for Dose Group 3

(for time points refer to [Flow Chart](#))

C: parameters to be determined at Visit 4 (end of trial examination)

The tests listed in [Table 5.2.3: 2](#) are exclusionary laboratory tests that may be repeated as required. The results will not be entered in the CRF/database and will not be reported in the CTR. Except for drug screening, it is planned to perform these tests during screening only. Drug screening will be repeated throughout the study (see [Flow Chart](#)).

Proprietary confidential information © 2020 Boehringer Ingelheim International GmbH or one or more of its affiliated companies

Table 5.2.3: 2      Exclusionary laboratory tests

Functional lab group	Test name
Drug screening (urine)	Amphetamine/MDA Barbiturates Benzodiazepine Cannabis Cocaine Methadone XTC Opiates Phencyclidine Tricyclic antidepressants Alcohol
Infectious serology (blood)	Hepatitis B surface antigen (qualitative) Hepatitis B core antibody (qualitative) Hepatitis C antibodies (qualitative) HIV-1 and HIV-2 antibody (qualitative)
Pregnancy test (serum)	Beta human chorionic gonadotropin (beta-HCG)
Postmenopausal Status (blood)	FSH, estradiol

The results of the drug screening and alcohol test will not be included in the CTR.

The laboratory tests listed in [Table 5.2.3: 1](#) and [5.2.3: 2](#) will be performed at the safety laboratory of 

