#### 5.2.6.1.4 Adverse events of special interest

The term adverse events of special interest (AESI) relates to any specific AE that has been identified at the project level as being of particular concern for prospective safety monitoring and safety assessment within this trial, e.g. the potential for AEs based on knowledge from other compounds in the same class. AESIs need to be reported to the sponsor’s Pharmacovigilance Department within the same timeframe that applies to SAEs, please see [Section 5.2.6.2.2](#).

The following are considered as AESIs:

- Hepatic injury

A hepatic injury is defined by the following alterations of hepatic laboratory parameters:

- o An elevation of AST (aspartate transaminase) and/or ALT (alanine transaminase)  $\geq 3$ -fold ULN combined with an elevation of total bilirubin  $\geq 2$ -fold ULN measured in the same blood sample, or
- o Aminotransferase (ALT, and/or AST) elevations  $\geq 10$  fold ULN

These lab findings constitute a hepatic injury alert and the subjects showing these lab abnormalities need to be followed up according to the 'DILI checklist' provided via eDC. In case of clinical symptoms of hepatic injury (icterus, unexplained encephalopathy, unexplained coagulopathy, right upper quadrant abdominal pain, etc.) without lab results (ALT, AST, total bilirubin) available, the Investigator should make sure that these parameters are analysed, if necessary in an unscheduled blood test. Should the results meet the criteria of hepatic injury alert, the procedures described in the DILI checklist should be followed.

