## **6.7 BASELINE, TIME WINDOWS AND CALCULATED VISITS**

Baseline is defined as the last available value assessed prior to first BI 1467335, placebo or phenelzine administration.

"Baseline" SBP used for comparison of TYR30 is defined as follows: Consider all SBP values within 35 min before tyramine administration on each tyramine testing day. If the SBP of the last 3 of these measurements are within a range of 10 mmHg, the mean of these 3 SBP values will be defined as baseline. If they are not within a range of 10 mmHg, the mean of all SBP values within 35 min before first tyramine administration will be defined as baseline. Baseline SBP is calculated prior to each tyramine testing day.

Time windows are defined in Section 6.1 of the CTP. Adherence to time windows will be checked at the RPM.

[figure not shown]

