### 7.8.3      **Vital signs**

The analyses of vital signs (blood pressure and pulse rate) will be descriptive in nature. Descriptive statistics of vital signs over time and for the difference from baseline (see [Section 6.7](#)) will be provided.

Unscheduled measurements of vital signs will be assigned to planned time points in the same way as described above for laboratory data. However, for vital signs, descriptive statistics will

be calculated by planned time point based on the last value of the subject at that planned time point (or assigned to that planned time point).

Clinically relevant findings in vital signs data will be reported as baseline conditions (prior to first administration of study treatment) or as AEs (after first administration of study treatment) if judged clinically relevant by the investigator, and will be analyzed as such.

Data from the BP monitoring will be listed. In addition, the maximum increase in SBP at TYR30 at screening and steady state will be analyzed descriptively. The maximum increase is defined as the highest change from the three SBP measurements used to attain TYR30, compared to the baseline SBP value used to calculate TYR30.

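### Unscheduled laboratory and vital-sign values taken after the first dose are summarised under the Day 1 pre-dose time point

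*SAP*

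**What the plan says.** SAP 7.8.2 starts from a premise: "Unscheduled measurements of laboratory data will be assumed to be repeat measurements of the most recent scheduled measurement". From this it concludes that "unscheduled measurements will be assigned to the planned time point of the previous scheduled measurement". Laboratory summaries by planned time point are then "based on the worst value of the subject at that planned time point (or assigned to that planned time point".

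SAP 7.8.3 follows suit: "Unscheduled measurements of vital signs will be assigned to planned time points in the same way as described above for laboratory data". The difference is that vital signs are summarised by the subject's last value at the time point, not the worst.

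Neither section makes an exception for values obtained after the first dose of study drug.

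Baseline is set elsewhere, in SAP 6.7: "Baseline is defined as the last available value assessed prior to first BI 1467335, placebo or phenelzine administration". That definition depends on when the value was actually assessed, not on the time point to which it is assigned.

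**The concern.** Treating an unscheduled value as a repeat is reasonable when it confirms the sample just before it. It is not reasonable when the first dose lies between the two. The scheduled Day 1 measurement is pre-dose, and several days pass before the next one. An unscheduled test in that gap is a new observation on drug, yet the rule files it as though it came from an untreated subject.

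Such tests are not ordered at random. When hepatic symptoms appear without laboratory results, Protocol 5.2.6.1.4 says that "the Investigator should make sure that these parameters are analysed, if necessary in an unscheduled blood test". A test of that kind does not fit the SAP's repeat-measurement premise.

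What is at stake is whether the tables of values over time are right. The Day 1 row is meant to describe subjects before treatment. It could contain on-drug values, while no on-treatment row contains them.

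**Working it through.** The plan states no figure to reproduce. The check sets the assignment rule beside the measurement schedule.

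**Step 1. Day 1 is pre-dose.** Both flow charts place the Day 1 assessments at 07:30 and the first dose at 08:00. Footnote 2 of each chart and Protocol 6.1 require completion within the 3 h before dosing. No later laboratory or vital-sign assessment is scheduled on Day 1.

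**Step 2. Next scheduled measurement of the same type.** The laboratory days come from the footnotes to Table 5.2.3: 1 in Protocol 5.2.3: Days 1, 14 and 28 for Dose Groups 1 and 2, and for phenelzine "parameters to be determined at Visit 3 on Day 1, 7 for Dose Group 3". The vital-sign days come from the flow charts: Day 7 for BI 1467335 or placebo, Day 3 for phenelzine. The BI/placebo admission on the afternoon of Day 6 carries only the urine drug and alcohol screen, so it does not shorten the window.

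**Step 3. Length of the window.** Hours from first dose = (day of next scheduled measurement − 1) × 24.

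| Measurement | Group | Next day | Window |
|---|---|---|---|
| Laboratory | BI 1467335 / placebo | 14 | 13 × 24 = 312 h (13 days) |
| Laboratory | Phenelzine | 7 | 6 × 24 = 144 h (6 days) |
| Vital signs | BI 1467335 / placebo | 7 | 6 × 24 = 144 h (6 days) |
| Vital signs | Phenelzine | 3 | 2 × 24 = 48 h (2 days) |

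These agree with the flow-chart clock (Day 3 = 48:00, Day 7 = 144:00, Day 14 = 312:00). Each window may close up to 3 h earlier, because the next assessment is also pre-dose. For laboratory tests it covers about 13 of up to 39 treatment days (33%), or about 6 of up to 19 (32%).

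**Step 4. Effect within the window.** An on-drug laboratory value displaces the true pre-dose value in the Day 1 summary whenever it is worse. An on-drug vital sign always displaces it, being the later of the two.

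**Step 5. Effect on the Day 1 row.** If one subject out of n has an on-drug value d above the pre-dose value, the Day 1 mean moves by d/n. With 16 subjects in an active BI 1467335 arm this is 0.0625 × d; with 14 on phenelzine it is 0.071 × d. As an assumed example, take ALT 20 U/L pre-dose and 200 U/L on Day 5:

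- d = 200 − 20 = 180 U/L.
- Shift in the Day 1 mean with n = 16: 180/16 = 11.25 U/L.
- The SAP 6.7 baseline stays at 20 U/L. If the other 15 subjects have Day 1 values equal to baseline, the Day 1 row shows a mean difference from baseline of +11.25 U/L at a time point before any drug was given.
- The 200 U/L value appears at no on-treatment time point.

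**Step 6. The second boundary.** The last scheduled laboratory sample before the steady-state challenge is Day 28 (BI/placebo) or Day 7 (phenelzine). The next is the end-of-trial visit. Unscheduled laboratory values on Days 29 to 39, or Days 8 to 19, are therefore filed under a pre-tyramine time point. From the first Visit 3 tyramine dose they belong to the drug-plus-tyramine phase of SAP Table 6.1: 1.

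**The case against.** The best defence is that little depends on this row. Most of that defence stands, and it rules out three stronger conclusions that a reader might draw.

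- **That the rule corrupts baseline or contradicts SAP 6.7.** It does not. Baseline is the last value actually assessed before first study drug, so a Day 5 value cannot become baseline.
- **That it shrinks the on-treatment change.** SAP 7.8.2 and 7.8.3 take differences from the SAP 6.7 baseline. In the example, the Day 14 change is still measured from 20 U/L. An apparent fall after Day 1 could arise only from comparing raw means down the rows, and the same Day 1 row would show the 200 U/L as its maximum, because SAP 7 includes the maximum among its standard statistics.
- **That it hides a safety signal.** Clinically relevant findings after first dosing are reported and analysed as adverse events, which are assigned to phases by date and time. Hepatic injury has its own table as an event of special interest, and all individual values are listed.

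Nor is it established that the value would be counted in the pre-treatment period. Protocol 7.3.4 links measurements to treatment by planned time, which points that way. However, it leaves the detail to the SAP, and SAP 6.1 bases the additionally displayed actual treatments on the date/time phases. The documents allow either reading.

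Two further points are fair. The number of unscheduled values is not given, and it may be small while BI/placebo subjects are at home after the first dose. Also, the ADS Plan and the sponsor's laboratory-data standard, which are not among these documents, may already contain a limit.

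None of this repairs the rule as written. Followed literally, it presents on-drug values as pre-dose values.

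**Conclusion.** The point holds, with a narrow reach. SAP 7.8.2 and 7.8.3 give a rule that is wrong as written: it carries values back across the first dose and, for laboratory tests, across the start of the steady-state tyramine challenge. The damage is limited to the by-time-point descriptive tables for laboratory data and vital signs. Within them, the Day 1 row can mix pre-dose and on-drug values and can show a non-zero difference from baseline before treatment.

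The windows show when misfiling is possible, not how often it happens. If no unscheduled value falls inside them, no table changes. The laboratory windows rest on explicit protocol text, while the vital-sign windows rest on a reading of the flow-chart columns. The ALT figures are an assumption chosen to show the mechanism. The correction is worth making because it costs almost nothing.

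**What to change.** Amend SAP 7.8.2 and 7.8.3 so that:

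- an unscheduled value inherits the previous planned time point only if both measurements fall in the same analysis phase of Table 6.1: 1, judged by actual date and time;
- a value taken after first study drug is never assigned to a pre-dose time point;
- a value that fails these conditions is shown in a separate row, either unscheduled on-treatment or worst on-treatment.

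Such values should not be moved forward to the next scheduled day. Filing a Day 5 result under Day 14 would also misstate its timing.

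The same-phase condition deals with both boundaries, first dosing and the start of the steady-state challenge. The cost is a short addition to each section, one condition in the time-point mapping program and an extra table row where needed. No new data are required. If the ADS Plan or the laboratory-data standard already imposes this limit, stating it in the SAP is enough.

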### 7.8.3      **Vital signs**

The analyses of vital signs (blood pressure and pulse rate) will be descriptive in nature. Descriptive statistics of vital signs over time and for the difference from baseline (see [Section 6.7](#)) will be provided.

Unscheduled measurements of vital signs will be assigned to planned time points in the same way as described above for laboratory data. However, for vital signs, descriptive statistics will

be calculated by planned time point based on the last value of the subject at that planned time point (or assigned to that planned time point).

Clinically relevant findings in vital signs data will be reported as baseline conditions (prior to first administration of study treatment) or as AEs (after first administration of study treatment) if judged clinically relevant by the investigator, and will be analyzed as such.

Data from the BP monitoring will be listed. In addition, the maximum increase in SBP at TYR30 at screening and steady state will be analyzed descriptively. The maximum increase is defined as the highest change from the three SBP measurements used to attain TYR30, compared to the baseline SBP value used to calculate TYR30.

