#### Procedure-related risks

The use of an indwelling venous catheter or venepuncture for e.g. blood sampling may result in mild bruising, and in rare cases, in transient inflammation of the wall of the vein, or nerve injury, potentially resulting in paraesthesia, reduced sensibility, and/or pain for an indefinite period.

The total volume of blood withdrawn per subject during the entire study will be approximately 500 mL and thus does not exceed the volume of a normal blood donation (500 mL). No health-related risk to healthy subjects is expected from withdrawal of this volume of blood.

As part of the screening procedure, subjects will receive increasing oral doses of up to 700 mg tyramine. Under physiological conditions alimentary tyramine is completely inactivated by intestinal MAO-A, due to the limited amount of tyramine in food. For the challenge test, it is intended to exceed the individual intestinal MAO A capacity to achieve a systemic availability of oral tyramine. Tyramine acts as an indirect sympathomimetic agent by displacing noradrenaline from vesicles of adrenergic nerves. This leads to vasoconstriction and increase in blood pressure, and may cause headache and even hypertensive crisis [R19-1599]. Due to the design of the planned study with a shallow dose escalation, the stop of further tyramine dosing at TYR30, and the possibility to counteract the sympathomimetic effects with a non-selective  $\alpha$ -blocker, the risk of overshooting sympathomimetic effects (in particular the risk for hypertensive crisis) is considered remote. This should be also true for the occurrence of cardiac events by only including young healthy subjects at the age of  $\leq 45$  years.

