## **5.6 OTHER ASSESSMENTS**

### **5.6.1 Tyramine challenge**

Tyramine challenge will be conducted predose (Day -10 to Day -1) and during steady state (Day 8 to Day 19 for Dose Group 3, Day 29 to Day 39 for Dose Groups 1 and 2).

Before start of the tyramine challenge, subjects have rested for at least 5 min in a supine position. Systolic and diastolic blood pressures (BP) will be measured by a blood pressure monitor (Mortara Surveyor S12). Blood pressure will be measured approximately every 5 minutes during the 35 minutes preceding tyramine administration to determine the baseline SBP, i.e. mean of 3 consecutive measurements with a maximum range of 10 mmHg. If a stable SBP will not be obtained within the 35 minutes, the mean of all 7 readings will be used as the baseline value.

After baseline SBP has been established, fasted subjects will receive a single oral dose of tyramine. Tyramine doses will be escalated from 10 mg to 700 mg QD (10, 25, 50, 100, 200, 300, 400, 500, 600, and 700) on a daily basis. After each tyramine administration blood pressure will be again measured beginning 5 minutes after tyramine dosing and approximately every 5 minutes thereafter for at least 2 hours and then approximately every 15 minutes for additional 2 hours. For each subject, the tyramine dose escalation will be stopped when an increase of systolic blood pressure (SBP)  $\geq$  30 mmHg for at least 3 consecutive measurements is measured (i.e. TYR30). Participants who will not attain the predefined target elevation in SBP within 4 hours after the highest tyramine dose (700 mg) will not be included in the study.

At steady state the tyramine challenge test will be repeated, starting with a lower tyramine dose of 5 mg in all dose groups. Further tyramine dose escalation is identical to the predose regimen, apart from an intermediate dose of 150 mg only exclusively in the phenelzine group. Subjects will continue with their assigned treatment (BI 1467335 or placebo, or phenelzine) which is administered simultaneously to the tyramine dose. For each subject, the tyramine dose escalation will be stopped as soon as TYR30 has been established (increase of SBP  $\geq$  30 mmHg for at least 3 consecutive measurements). In none of the subjects the tyramine dose will exceed 700 mg, even if TYR30 has still not been established.

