### 7.8.1 Adverse Events

AEs will be coded with the most recent version of MedDRA.

The analyses of AEs will be descriptive in nature. All analyses of AEs will be based on the number of subjects with AEs and not on the number of AEs.

For further details on summarization of AE data, please refer to "Analysis and Presentation of Adverse Event Data from Clinical Trials" ([7](#)) and "Handling of missing and incomplete AE dates" ([3](#)).

The analysis of AEs will be based on the concept of treatment emergent AEs. That means that all AEs will be assigned to screening, on-treatment or follow-up phases as defined in [Section 6.1](#). AEs will be analysed based on actual treatments, as defined in [Table 6.1: 1](#).

An overall summary of AEs will be presented. This overall summary will comprise summary statistics for the class of other significant AEs according to ICH E3 ([8](#)) and for the class of AESIs.

**CTP:** *The following are considered as AESIs:*

- *Hepatic injury*  
*A hepatic injury is defined by the following alterations of hepatic laboratory parameters:*
  - *An elevation of AST (aspartate transaminase) and/or ALT (alanine transaminase)  $\geq 3$ -fold ULN combined with an elevation of total bilirubin  $\geq 2$ -fold ULN measured in the same blood sample, or*
  - *Aminotransferase (ALT, and/or AST) elevations  $\geq 10$  fold ULN*

The investigator had to classify on the eCRF whether an observed AE was an AESI or not.

According to ICH E3 ([8](#)) AEs classified as "other significant" need to be reported and will include those non-serious and non-significant AEs

- (i) which are marked haematological or other lab abnormalities, or
- (ii) which were reported with "action taken = discontinuation" or "action taken = reduced", or
- (iii) which lead to significant concomitant therapy as identified by the Clinical Monitor/Investigator at a Medical Quality Review Meeting.

The frequency of subjects with AEs will be summarised by treatment, primary SOC and preferred term. AEs which were considered by the investigator to be drug related will be summarised separately. Separate tables will also be provided for subjects with SAEs, subjects with AESIs and subjects with other significant AEs (according to ICH E3 ([8](#))). AEs will also be summarized by maximum intensity.

The SOCs and preferred terms within SOCs will be sorted by descending frequency over all treatment groups.

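### SAP 7.8.3 takes the maximum SBP increase from only the three readings that establish TYR30, so a higher value later that day is missing from the only visible peak-SBP summary

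*SAP*

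**What the plan says.** SAP 7.8.3 handles the challenge blood pressures in two ways. First, "Data from the BP monitoring will be listed". Second, "the maximum increase in SBP at TYR30 at screening and steady state will be analyzed descriptively", with this definition: "The maximum increase is defined as the highest change from the three SBP measurements used to attain TYR30". The change is taken from the baseline used for TYR30, and SAP 6.7 derives that baseline separately for every challenge day: "Baseline SBP is calculated prior to each tyramine testing day".

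Protocol 5.6.1 collects far more than three readings. They begin 5 minutes after the dose and continue "approximately every 5 minutes thereafter for at least 2 hours and then approximately every 15 minutes for additional 2 hours". TYR30 requires a rise of at least 30 mmHg on at least three consecutive readings. It stops the dose escalation; nothing in 5.6.1 stops the monitoring that day. The same section foresees subjects who never qualify on treatment: "In none of the subjects the tyramine dose will exceed 700 mg, even if TYR30 has still not been established".

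Protocol 1.4 names the hazard that a peak summary would describe and rates it: "the risk of overshooting sympathomimetic effects (in particular the risk for hypertensive crisis) is considered remote".

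**The concern.** The three qualifying readings are the point at which the response has only just met the criterion. If SBP is still climbing then, the peak comes later and is not counted, although the quantity is called a maximum. The shortfall can only go one way, because the highest of three readings cannot exceed the highest of all readings that day. It is likely to be larger when the response is larger, and those responses matter most for safety.

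The sponsor treats overshoot as a real design issue. Protocol 1.4 relies on shallow escalation, stopping at TYR30 and an available alpha-blocker, and the phenelzine ladder has an extra 150 mg step. A reader who wants to know how high SBP went by arm, above all on phenelzine, would have to work it out from listings.

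**Working it through.** The documents state no figure on this point, so there is none to reproduce. The check compares what is collected with what is summarised.

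**Readings per challenge day** (Protocol 5.6.1):
- 5 to 120 min, every 5 min: 120 / 5 = 24.
- 135 to 240 min, every 15 min: 8.
- Total 24 + 8 = 32, approximate because the protocol's times are approximate.

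**Share used on the TYR30 day:** 3 / 32 = 9.4%.

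**Scheduled readings after the third qualifying one** (32 minus those already taken):

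| Third qualifying reading at | Taken so far | Still to come, unused |
|---|---|---|
| 15 min | 3 | 29 |
| 30 min | 6 | 26 |
| 60 min | 12 | 20 |
| 120 min | 24 | 8 |
| 240 min | 32 | 0 |

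This assumes that monitoring runs to 4 h on the TYR30 day, and that the three readings are the first three of the run. The SAP does not say which three count when the run is longer, but the first three is the natural reading.

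**Subjects without TYR30 at steady state.** The ladder has 11 steps for BI 1467335 and placebo (5, 10, 25, 50, 100, 200, 300, 400, 500, 600, 700 mg) and 12 for phenelzine (150 mg added). Such a subject contributes 0 of 11 × 32 = 352 scheduled readings, or 0 of 12 × 32 = 384. At screening the gap does not arise, because subjects who miss TYR30 at 700 mg are not included.

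**Other visible routes:**
- Vital signs by planned time point (SAP 7.8.3) use the last value at each time point. Protocol 5.2.2 assigns them to a different monitor. The table shows a maximum across subjects at each time, not each subject's peak.
- SAP 7.4.2 summarises TSF and the TYR30 doses only.
- AEs capture a rise only if the investigator judges it clinically relevant.

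None of these is a per-subject peak.

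**Illustration only; these inputs are not from the documents.** Assume a rise of peak × [(t/75)·exp(1 − t/75)]³ with t in minutes, reading noise SD of 4 or 6 mmHg, baseline error SD equal to the noise SD / √3, and 20,000 simulated days per case. Means in mmHg on days that reach TYR30 (SD 4; SD 6):

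| True peak | Three-reading maximum | All-readings maximum | Gap |
|---|---|---|---|
| 35 | 37.6; 40.2 | 40.2; 44.0 | 2.7; 3.8 |
| 45 | 41.2; 43.6 | 49.5; 52.5 | 8.4; 8.9 |
| 60 | 46.2; 47.9 | 64.3; 67.0 | 18.0; 19.1 |

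The gap is not all understatement. At a true peak of 60 the three-reading mean is about 12 to 14 too low and the all-readings mean about 4 to 7 too high. At 35 both are too high, because noise inflates any maximum. The pattern supports showing both values; it does not give a size for this trial.

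**The case against.** The best case for the plan is that SAP 7.8.3 names its quantity as the increase at TYR30, defines it exactly and never calls it a daily peak. The protocol promises no peak-SBP table. Much is covered elsewhere: the readings are listed, and AEs are tabulated by tyramine phase (SAP Table 6.1: 1) and by maximum intensity. Non-serious AEs "which lead to significant concomitant therapy as identified by the Clinical Monitor/Investigator" are tabulated separately (SAP 7.8.1). All of that stands, and it keeps the point optional.

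Several stronger readings are tempting and are not supported:

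- **Overshoot is hidden.** It is not. It is left unsummarised beyond the third reading, and the listings hold it.
- **Brief rises are a serious omission.** A rise on one or two readings fails the plan's own three-reading criterion, so leaving it out is consistent with the design. For the same reason, a subject who never reaches TYR30 has had no sustained rise of 30 mmHg. What is missing there is a value in the table, not evidence of a large response.
- **The counts measure bias.** 3 of 32 and 0 of 352 describe coverage. Many of those readings come from low doses where little response is expected.
- **No other blood-pressure summary exists.** Parts of both documents are redacted next to the safety endpoints and their analysis, so the statement holds for visible text only.
- **Each subject's highest value over all challenge days should be compared between arms.** That is not like for like. TYR30 at 25 mg gives 3 steady-state days (3 × 32 = 96 readings), while TYR30 at 500 mg on the BI/placebo ladder gives 9 (9 × 32 = 288). More readings raise a maximum mechanically.

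**Conclusion.** The point holds as a minor improvement to safety reporting. In the visible text, the only peak-SBP summary stops at the third qualifying reading. It therefore omits any higher value later on the TYR30 day and has no steady-state entry for a subject without TYR30 at 700 mg. On the scheduled times it uses 3 of about 32 readings.

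How far this lowers the reported peak, in mmHg, cannot be derived from the documents. It depends on when TYR30 is reached and on the shape of the response afterwards. TSF, the ANOVA and the sample size are unaffected. The conclusion assumes that monitoring continues to 4 h as Protocol 5.6.1 schedules, and that no redacted section already contains a peak summary.

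**What to change.** In SAP 7.8.3:

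1. Define the maximum SBP increase as the highest change from that day's baseline (SAP 6.7) over all post-dose readings up to 4 h on the TYR30 day. If TYR30 is not reached, use the last challenge day, for example 700 mg, and show the dose given.
2. Summarise it by treatment at screening and at steady state.
3. Keep the three-reading value alongside under its own name, such as increase at attainment of TYR30, and state which three readings count when the run is longer.
4. Flag subjects given an alpha-blocker or other rescue therapy that day, since later readings may be blunted. Protocol 4.2.2.1 already records such therapy with its time of intake on study days.
5. Do not add a maximum across challenge days for comparison between arms.

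The cost is one derivation and one descriptive table from readings already collected. Trial conduct, the TYR30 definition and the primary analysis do not change. The downside is that a maximum over about 32 readings picks up more single-reading noise than a maximum over three, which is why both values should appear together and the active arms be read against placebo.
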